#### **4.3 Lead-In Phase**

ABSORB III will include a Lead-In Phase that will provide an opportunity to evaluate whether the Absorb physician training, developed from the ABSORB programs outside the US, can be applied to US clinical practice.

The Lead-In Phase will enroll/register subjects prior to the randomization of the 2000 subjects supporting the primary analysis. The objective of the Lead-In Phase will be the evaluation of the applicability and transferability of the didactic Absorb BVS physician training plan to US clinical practice. The primary area of learning in the usage of Absorb BVS includes the vessel sizing, lesion preparation, device delivery and deployment, as these variables reflect the change in practice that occurs with the use of a polymeric scaffold compared to a metallic stent. The Lead-In Phase will involve up to 35 US sites and up to 50 subjects treated with Absorb BVS.

There will be four key areas of evaluation of the Lead-In Phase, 1) angiographic inclusion/exclusion, 2) vessel sizing meeting protocol required criteria, 3) treatment strategy per protocol requirements and 4) device success. Each of these variables will provide a measure of adherence to the physician training program. The data for each registered subject will be collected through the electronic case report forms (eCRFs). The outcomes will determine whether the physician training requires further modification to meet the needs of the US physicians. Details on how the sponsor will evaluate the Lead-In Phase can be found in Appendix VII.

The first Absorb BVS case for each investigator participating in the Lead-In will be attended by an Abbott Vascular (AV) CRA. The objective of the CRA-attended cases is to provide an opportunity for the investigator to receive guidance on and reinforcement of the Absorb BVS teachings (detailed in **Section 4.2**) during their Absorb BVS enrollment. The CRA field group will be trained on Device Handling Fundamentals and all elements of the protocol. At the time of the procedure, the CRA attendant will be available to provide review of the key protocol requirements and device usage elements prior to the start or during the index procedure. The sponsor CRA will make every attempt to ensure that the first Absorb BVS case is attended in person. However, a diagnostic angiogram is often not performed on a separate date prior to PCI for pre-screening. In these instances, since the diagnostic catheterization (qualifying cardiac catheterization) and the intervention are done at the same setting (with limited amount of time in-between), AV would be unable to travel to the site and attend in person. For these sites, AV personnel will be available to provide telephone guidance and reinforcement prior to the start of the index procedure.

Prior to the index procedure, the CRA will review the 4 variables with the enrolling physician: 1) angiographic inclusion/exclusion criteria requirements; 2) vessel treatment strategy; 3) appropriate vessel sizing and scaffold selection; and 4) appropriate device preparation and usage. If the CRA is at the site in person, once this information is reviewed and the index procedure has occurred, the CRA will complete the Lead-In checklist for the investigator and submit this information to AV for filing. If the CRA is not present, the site will be requested to complete the eCRF within 1-2 business days of the procedure, which will be remotely monitored by the CRA within 1-2 business days of data entry. If the CRA is present at the time of the index procedure, the site will have 2 business days to enter the subject data into the eCRF.

[figure not shown]
In addition to the CRA guidance provided onsite or via telephone, during the site initiation visit, the site will be provided with a similar checklist and reference tools in order to ensure that they have the necessary information readily available to ensure appropriate subject selection, vessel treatment strategy, vessel sizing and Absorb BVS selection as well as appropriate device preparation and usage.

Angiograms should be submitted to the core laboratory within 2 business days following the procedure for analysis to ensure appropriate vessel sizing and scaffold usage (for details on imaging uploading refer to **Imaging Guidance Document**). This feedback will be provided to the site within 72 hours of submitting the angiogram. If discrepancies are identified by the angiographic core laboratory specific to vessel sizing and the %DS required for analyzing device success (< 30%), the angiographic core laboratory and the CRA, respectively, will contact the investigator to discuss the issue and any corrective measures necessary to avoid the issue in future cases. Investigators not meeting all four criteria (CRA assessed and core laboratory assessed), will be retrained on the missed elements by the AV CRAs and/or core laboratory if necessary prior to their next Absorb BVS case. Depending on the elements missed, the CRA may attend the next Absorb BVS case to ensure criteria are met. At any time during the Lead-In phase, if AV or the site determines that further site/investigator training is required, such training will be arranged.

[figure not shown]
#### **4.4 ABSORB III Treatment Flow and Lesion Selection**

The same treatment flow and lesion selection applies to all subjects in ABSORB III (including the Lead-In Phase and the Imaging Cohort). Either one or two target lesions in two separate epicardial vessels will be treated. If only one target lesion is intended, a second non-target lesion in a different epicardial coronary artery than the target lesion may also be treated prior to the target lesion. For the Lead-In Phase, only Absorb BVS will be used for target lesion (s).

**Figure 4.1** shows the lesion treatment for subjects in the Lead-In Phase.

**Figure 4.2** shows the lesion treatment for the 2200 randomized subjects.

If a non-target lesion is present, the non-target lesion must be successfully treated first with a XIENCE stent. Despite the allowance of two lesion treatment, planned staged procedures are not allowed in ABSORB III.

Prior to treatment with the assigned device (Absorb BVS or XIENCE), vessel sizing by visual estimation must be conducted to appropriately match the device to the size of the vessel. Quantitative methods such as on-line QCA, IVUS or OCT may be used if deemed necessary per physician discretion, but are not required. Details on the vessel sizing methods can be found in **Imaging Guidance Document** (detailed in **Section 7.3.2**).

**Table 4.1** provides the device sizes, RVD and lesion length for ABSORB III.

**Table 4.1 Absorb BVS and XIENCE Sizes**

Device	Lesion and Device Sizes	
	RVD 	Lesion Length 
Lead-In Absorb BVS (Target lesion)	RVD $\geq$ 2.75 mm - $\leq$ 3.25 mm Scaffold diameter: 3.0 mm	Lesion length $\geq$ 8- $\leq$ 14 mm Scaffold length: 18 mm
RCT Absorb BVS (Target lesion)	RVD $\geq$ 2.50 mm - $\leq$ 3.75 mm Scaffold diameter: 2.5, 3.0 and 3.5 mm	Lesion length $\leq$ 24 mm Scaffold Length  : 8, 12, 18 and 28 mm 
RCT XIENCE  (Target lesion)	RVD $\geq$ 2.50 mm - $\leq$ 3.75 mm Stent diameter: 2.5, 2.75, 3.0, 3.25, 3.5, 4.0 mm	Lesion length $\leq$ 24 mm Stent Length: 8, 12, 15, 18, 23 and 28 mm 
XIENCE (Non-target lesion)	Per IFU (RVD $\geq$ 2.25 mm - $\leq$ 4.25 mm can be treated) All available sizes	Per IFU (lesion $\leq$ 32 mm)  All available sizes

 Reference vessel diameter (RVD) and lesion length based on visual estimation

 Both the 8 mm and 12 mm lengths will be available for the 2.5/3.0 diameter Absorb BVS. Only the 12 mm length will be available for the 3.5 mm diameter. The commercially approved CE marked 23 mm Absorb BVS device will not be used in this study.

 For target lesion, planned overlapping is not allowed (i.e., the lesion must be eligible for treatment with a single stent). However, bailout overlapping is allowed if required.

 For non-target lesion, planned overlapping allowed.

 XIENCE V, XIENCE Prime, XIENCE Xpedition, XIENCE Alpine, XIENCE Pro, and XIENCE ProX are used in this study.

The commercially approved CE marked 23mm Absorb BVS device will not be used in this study.

A minimum of 2 mm (by visual estimation) of minimally diseased tissue should be covered by the device at both the proximal and distal edges.

Planned overlap of the target lesion is not allowed. Overlap in the case of bailout is allowed for both the target and non-target lesion. Please refer to **Section 7.3.5** for details regarding bailout.

#### **4.5 Measures Taken to Avoid and Minimize Bias**

In ABSORB III there will be several measures taken to avoid and minimize bias such as randomization and blinding. This process has been detailed in the following sections.

### **4.5.1 Randomization**

#### **Stratified Randomization:**

Approximately 2000 subjects will be randomized 2:1 in the primary analysis (test device: Absorb BVS vs. control device: XIENCE). As diabetes and dual lesion treatment are known risks that may influence the rate of the composite endpoint (TLF), subjects will be stratified by diabetes mellitus (diabetic vs. non-diabetic) and dual vessel treatment (single target lesion vs. dual target lesion vs. one target lesion and one non-target lesion). Subjects will also be stratified by site at some pre-specified sites (expected high-enrolling sites). Other sites will be combined to ensure a sufficient number of subjects for the attainment of the desired randomization ratio. In the Imaging Cohort for both subjects receiving IVUS and those receiving the OCT, randomization (2:1) will be stratified by diabetes mellitus (diabetic vs. non-diabetic) and intended dual vessel treatment (single target lesion vs. dual target lesion vs. one target lesion and one non-target lesion). A centralized randomization service, IVRS, will be used.

#### **Timing of Randomization:**

Randomization will be done after successful treatment of the non-target lesion (if any) and successful and uncomplicated pre-dilatation of the target lesion (or the first target lesion if there are two target lesions) and vessel sizing (refer to **Section 7.3.4, Treatment Rules of the Target Lesion**, for details). Once randomization is completed and a treatment is assigned, crossover is not permitted. Regardless of the actual device the subject received, the subject will be included in ITT population per the original randomization assignment. An Absorb BVS scaffold may never be used in a patient randomized to XIENCE. However, if the patient is randomized to Absorb BVS and the scaffold cannot be delivered or a complication otherwise develops that requires treatment with a XIENCE stent, a XIENCE or any other stent may be used as necessary in the best interests of the patient.

The subject is considered to be successfully registered in this study and considered in the ITT population at the point of randomization (refer to Section 6.4). Lead-In subjects will be considered registered in the study upon calling IVRS. Refer to Appendix IV (Figure 1 and 2) for enrollment and registration timeline and flow chart.

### **4.5.2 Blinding**

This is a single-blinded clinical trial. Subjects will be blinded to their treatment assignment and the study site personnel will be trained not to disclose the treatment assignment to the subject. Additionally, blinded site personnel, not present at the index procedure, will be assigned to conduct the clinical follow-up and they will be provided with a standard follow-up interview script in order to reduce bias and maintain subject blinding. Subject blinding should be maintained until the 5-year follow-up visit for all subjects is completed.

The physician performing the procedure will not be blinded to the assigned treatment. Thus, if a clinical follow-up with a study physician is deemed necessary at the protocol required follow-up time points, a different physician (or designee) than the one who implanted the device(s) should conduct follow-up clinical visits in order to maintain subject blinding. However for the Imaging Cohort, the protocol-required imaging follow up can be done by the same physician who implanted the device. Site personnel will be adequately trained such that the physician (or

designee) conducting the clinical follow-up is adequately blinded to the treatment received by the subject. For unscheduled visits, subjects may see the physician who implanted the device(s). Treating physicians should conduct all non-protocol related visits with the subject with caution, to prevent unblinding of the subject.

The Clinical Events Committee (CEC) will be blinded to the randomization assignments. The angiographic, IVUS and OCT core laboratories cannot be blinded to the device received. The Data Safety Monitoring Board (DSMB) will also be blinded to the subject's randomization. Independent statisticians will generate blinded tables for review by the DSMB. The DSMB may request unblinded data if a safety signal is observed.

Sponsor personnel that will be unblinded will be the independent biostatisticians involved in generating and verifying the randomization code, key Clinical Science and Operations, Clinical Safety Monitor, Site Monitors, Clinical Data Management, Electronic Database Programmer, Inventory Management staff, and Clinical Information System (IS) personnel working on the trial. Restricted access of blinded personnel to the clinical database will be maintained until unblinding of the study.

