## **12.7 Committees**

### **12.7.1 Steering Committee**

The Steering Committee is assigned by the Sponsor and comprises the Study Chairman and Principal Investigators, as specified on the cover page of this protocol. Other physician scientists may be added to the steering committee. The Sponsor will be represented by at least one person each from the Clinical Science and Clinical Program Management groups. The directors of the core laboratories and other Sponsor's personnel may also participate in the Committee meetings if appropriate. Meeting minutes from this committee will be filed with the Sponsor.

The Steering Committee is responsible for overseeing the scientific and operational aspects of the study. This committee will meet regularly to monitor patient enrollment, general data collection and non-compliance with the investigation plan at individual centers, to review and act upon recommendations of the Data and Safety Monitoring Board, to review operational issues that may arise and warrant a protocol amendment or other corrective action and to determine policy regarding any publications arising from data generated from the performance of the study.

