The device should only be used by physicians who have been trained in interventional cardiology. The selected investigators will be trained on the device prior to participating in the study. In addition, they and other hospital personnel who are participating in a clinical trial will be trained on the IFU and clinical trial protocol.

The patients will be screened against the inclusion and exclusion criteria before enrollment in the trial. The patients will be evaluated clinically with or without imaging at pre-determined time points per clinical trial protocol requirements to assess their clinical status.

Corrective and preventative actions will be implemented by Abbott Vascular, as necessary, if deviations from recommendations in the protocol or IFU are observed.

All device deficiencies, commercial complaints, and adverse events from clinical trials are monitored internally by Abbott Vascular. An independent Data Safety Monitoring Board (DSMB) will monitor safety throughout the clinical trial. Stopping rules will be discussed with the DSMB and applied for subject safety through enrollment.

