The Clinical Events Committee (CEC) will be blinded to the randomization assignments. The angiographic core laboratories cannot be blinded to the device received. The Data Safety Monitoring Board (DSMB) will also be blinded to the subject’s randomization. Independent statisticians will generate blinded tables for review by the DSMB. The DSMB may request unblinded data if a safety signal is observed.

Sponsor personnel that will be unblinded will be the independent biostatisticians involved in generating and verifying the randomization code, key Clinical Science and Operations, Clinical Safety Monitors, Site Monitors, Clinical Data Management, Electronic Database Programmer, Inventory Management staff, and Clinical Information System (IS) personnel working on the trial. Restricted access of blinded personnel to the clinical database will be maintained until unblinding of the study.

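### The DSMB's only stated route to by-arm data is a request after an undefined safety signal, which pooled tables may not reveal for rare events

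*Combined protocol and SAP*

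**What the plan says.** ABSORB III section 4.5.2 sets three rules in sequence. The board is masked: "The Data Safety Monitoring Board (DSMB) will also be blinded to the subject's randomization". It works from masked output: "Independent statisticians will generate blinded tables for review by the DSMB". Access to assignment is conditional: "The DSMB may request unblinded data if a safety signal is observed". ABSORB IV section 4.4.2 repeats all three.

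Neither section defines a safety signal, gives the table format or describes a closed report by arm. Section 8.4 of each trial leaves the board's procedures to a separate charter, which is not among the documents. It also makes the board's recommendations non-binding and leaves final decisions with the sponsor. On stopping, ABSORB III section 16.2 says only: "Stopping rules will be discussed with the DSMB and applied for subject safety through enrollment".

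The same blinding sections list sponsor staff who are unblinded. In ABSORB III the list includes "key Clinical Science and Operations, Clinical Safety Monitor, Site Monitors, Clinical Data Management", and ABSORB IV has an almost identical list. ABSORB III section 12.7.1 gives the sponsor Steering Committee seats for "at least one person each from the Clinical Science and Clinical Program Management groups". That committee acts on DSMB recommendations and reviews operational issues that may call for an amendment.

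**The concern.** Harm from Absorb relative to XIENCE is a difference between arms. Section 16.2 itself says that the adverse events and device issues of Absorb are not fully understood. A board that must observe a signal before it can ask for by-arm data depends on masked tables to produce that signal. If the tables are pooled, an excess on Absorb looks the same as a higher rate in both arms. For common events the overall rate may look high enough to prompt a request. For rare, serious events such as scaffold thrombosis it may not. At stake is whether the body meant to protect participants routinely sees the comparison that would show device harm.

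**Working it through.** The plan states no figure on this point, so there is none to reproduce. The check has two parts: what a blinded table can be under each allocation, and what a pooled table would show.

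**Inputs from the documents**
- ABSORB III: about 2000 subjects at 2:1, taken here as 1333 and 667. Planning TLF is 7.0% and the margin 4.5 points (section 10.3.1).
- ABSORB IV: about 2600 subjects at 1:1, or 1300 per arm. Planning 30-day TLF is 4.9% and the margin 2.9 points (section 10.3.1).
- XIENCE V definite/probable stent thrombosis: 0.3% in SPIRIT IV and 1.1% in SPIRIT III (ABSORB III section 2.1.10).

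**Assumptions.** The Absorb event rates and the 0.3% and 0.5% control thrombosis rates used below are illustrative.

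**Step 1: table format.** In ABSORB III, columns coded A and B would hold about 1333 and 667 subjects, so their sizes reveal the code. Tables that keep the blind must therefore be pooled. In ABSORB IV, coded columns of about 1300 each would keep the blind and still show an imbalance. The protocol does not say which format is used in either trial.

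**Step 2: TLF with Absorb exactly at the margin.**
- ABSORB III: 7.0 + 4.5 = 11.5%, and the pooled rate is (2 × 11.5 + 7.0)/3 = 10.0%.
- ABSORB IV: 4.9 + 2.9 = 7.8%, and the pooled rate is (7.8 + 4.9)/2 = 6.35%.

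Each pooled rate also fits equal rates in both arms, so attribution is impossible. To see whether the rate would be noticed at all, compare the pooled count with the planning rate by an exact one-sided binomial test at 0.025. A count is flagged at the smallest k for which P(X ≥ k | N, planning rate) ≤ 0.025.

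| Trial | N | Planning rate | k | Expected count | Chance of a flag |
|---|---|---|---|---|---|
| III | 2000 | 7.0% | 164 | 200 | 99.7% |
| III | 1000 | 7.0% | 87 | 100 | 92% |
| IV | 2600 | 4.9% | 150 | 165 | 90% |
| IV | 1300 | 4.9% | 80 | 83 | 63% |

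An excess of this size would usually show as a high overall rate.

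**Step 3: stent thrombosis in ABSORB III, threefold excess.**
- At 0.9% against 0.3%, the pooled rate is (2 × 0.9 + 0.3)/3 = 0.70%, or 14 events in 2000. Against a 1.1% background, k is 33 and the chance of a flag is about 0%. If the background were known to be 0.3%, k would be 12 and the chance 74%.
- At 1.5% against 0.5%, the pooled rate is (2 × 1.5 + 0.5)/3 = 1.17%, or about 23 events. Against 1.1%, the chance of a flag is about 3%. Against a known 0.5%, k is 18 and the chance 89%.

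The pooled table is informative only if the control rate is known closely, and the quoted range is nearly fourfold (1.1/0.3 = 3.7).

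**Step 4: what a by-arm table adds.** In the first case the expected split is 1333 × 0.009 = 12 against 667 × 0.003 = 2. With no difference, 14 events would split 9.3 to 4.7. A formal two-sided comparison at 0.05 has only about 30% power here, and about 50% in the second case. A by-arm report does not guarantee detection, but it shows the comparison without relying on an assumed background rate.

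**The case against.** The strongest reply is that the text does not say the tables are pooled. In the 1:1 trial, coded arms would show an imbalance. In the 2:1 trial, coded arms would show one too, at the price of the blind. A reader might infer that blinded tables can never show a signal and that the trigger is therefore circular. The documents do not support that. The format is unstated, individual serious events could count as a signal, and Step 2 shows that a margin-sized TLF excess would usually be noticed. This part of the reply stands and limits the concern to attribution and rare events.

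A second reply is that the rule is a permission rather than an exclusive condition, and that the charter may provide closed sessions. Section 8.4 also lets the board recommend termination on any perceived safety concern, whatever the statistical significance. These points are fair. Even so, no other route to by-arm data appears in either trial, and a charter that is more generous would conflict with the protocol sentence and need reconciling.

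A reader might also infer that unblinded sponsor staff steer amendments, and might point to ABSORB IV section 10.1, where a powered landmark analysis was removed. The documents do not support that. They do not say that the Clinical Science member of the Steering Committee is one of the unblinded key staff, or that those staff see outcomes by arm. They do not say who removed the landmark analysis, when, or with what data. The blinding sections also keep database access restricted for blinded personnel. All that remains is that no separation of these roles is described.

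Finally, some trialists prefer a masked board with unblinding on request. That is a legitimate design choice. It sits less well with a request that depends on an undefined precondition, in trials where the operators and many sponsor staff are already unblinded.

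**Conclusion.** The concern holds in limited form. In both trials the stated rule gives the DSMB no routine by-arm safety data and makes access depend on an undefined signal. If the tables are pooled, as truly blinded tables in ABSORB III would have to be, they cannot attribute an excess to an arm. They can also miss a threefold thrombosis excess: the chance of a flag against a 1.1% background is about 0% at 0.9% versus 0.3%, and about 3% at 1.5% versus 0.5%. A large TLF excess would usually be seen (99.7% in ABSORB III and 90% in ABSORB IV at full enrollment).

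These figures rest on the assumed arm rates, on pooled tables, and on a reader who compares the count with the planning rate or with the top of the quoted thrombosis range. The charter could narrow the gap but was not available. This is a low-cost improvement to safety monitoring and does not show that monitoring failed.

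**What to change.** 1. In ABSORB III section 4.5.2 and ABSORB IV section 4.4.2, delete the safety-signal condition. State instead that the independent statistician gives the DSMB a closed safety report by arm (deaths, TV-MI, ID-TLR and scaffold or stent thrombosis) at each scheduled review.
2. Bring the DSMB charter into line with that text. If the sponsor prefers a masked board, the minimum is to state the table format and allow by-arm access on request without a precondition.
3. Add one sentence saying that anyone who holds by-arm outcome data before database lock takes no part in amendment decisions. This asks for a clarification and does not imply that such involvement occurred.

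The cost is wording in the protocol and charter, since independent statisticians already prepare the DSMB's tables. The downside is that DSMB members are unblinded. No formal rule for stopping early for effectiveness is defined in either trial (ABSORB III section 10.4.9, ABSORB IV section 10.4.7), so by-arm safety review would not disturb a planned efficacy boundary.
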